14.5. Primary Analysis

Primary efficacy analysis:

The lens centration and lens movement outcomes will be converted to a binary response where 1= lens is centered or have optimal lens movement, and 0=otherwise.

The proportion of response ("1") will be analyzed using a generalized linear mixed model with a binary distribution and logit link function for all questions. Each model will include the experimental design factors: lens, period and lens by period interaction as fixed effects; and site and subject nested in site as random effects. Other baseline characteristics known to be important such as subject group (myope/hyperope), age, gender, and/or add power will be included as fixed covariates when appropriate. The covariance between residual errors from two eyes from the same subject at the same lens wearing period will be selected based on the finite-sample corrected Akaike's Information Criterion.⁶ Covariance structures considered may include: Homogenous compound symmetry (CS) and Unstructured covariance structure (UN). The structure that returns the lowest Akaike Information Criteria Corrected (AICC) will be selected as the structure that best fit the data.

Comparisons between the study lenses will be carried out using two-sided 95% confidence intervals of odds ratios (odds ratio calculated as Test / Control) for each individual question. Non-inferiority will be concluded if the lower limit is above 0.67. Superiority will be concluded if the lower limit is above 1.0.

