14.6. Secondary Analysis

Secondary efficacy analysis:

CLUE handling scores will be analyzed using a linear mixed model adjusting for baseline values as fixed covariates. The model will include the experimental design factors: lens, period and lens by period interaction as fixed effects. Other baseline characteristics known to be important such as subject group (myope/hyperope), age, gender, and/or add power will be included as fixed covariates when appropriate. The covariance between residual errors from the same subject across lens wearing periods will be selected based on the finite-sample corrected Akaike's Information Criterion.⁶ Covariance structures considered may include: Homogenous compound symmetry (CS) and Unstructured covariance structure (UN). The structure that returns the lowest Akaike Information Criteria Corrected (AICC) will be selected as the structure that best fit the data.

Comparisons between the Test lens and Control lens will be carried out using 95% confidence intervals constructed of least-square means (LSM) differences (Test minus Control) from the linear mixed model. The non-inferiority of the Test lens relative to the Control will be concluded if the lower confidence limit of LSM difference is above the non-inferiority margin -5. The superiority will be established if the lower confidence limit is above 0.

In all models, the Kenward and Roger method⁶ will be used for the calculation of the denominator of degrees of freedom.

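### The primary binary mixed model carries a free residual covariance that a Bernoulli outcome does not have, so its 95% interval for the lens odds ratio can undercover with 40 completers

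*Combined protocol and SAP*

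**What the plan says.** Section 14.5 reduces centration and movement to 1/0 per eye and models them with a "generalized linear mixed model with a binary distribution and logit link function". The fixed effects are lens, period and their interaction, with optional baseline covariates. The random part is "site and subject nested in site as random effects". A second layer of covariance is then added: "The covariance between residual errors from two eyes from the same subject at the same lens wearing period will be selected" between CS and UN. The rule is: "The structure that returns the lowest Akaike Information Criteria Corrected (AICC) will be selected". Non-inferiority is read from the lower limit of the two-sided 95% interval for the odds ratio (above 0.67), and superiority from the same limit (above 1.0).

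Section 14.6 closes with a statement that reaches back to the primary model: "In all models, the Kenward and Roger method" supplies the denominator degrees of freedom. Section 14.1 names SAS 9.4. No section names the estimation method for the binary model (pseudo-likelihood, Laplace or quadrature) or says whether the residual scale is held at 1.

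**The concern.** In a linear model the residual variance is a parameter, and choosing a covariance for it is ordinary practice. Section 14.6 does this for the CLUE handling score. Section 14.5 applies the same recipe to a yes/no outcome. Once the random effects are given, the variance of a Bernoulli response is p(1 - p) and nothing is left to estimate. A free residual variance is therefore not part of a proper likelihood. Because a subject effect is also in the model, the extra variance tends to be estimated below 1, which scales down the standard error of the within-subject lens contrast.

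Both primary hypotheses (section 2.3) and any superiority claim are decided by one limit of this interval, under the 5% error rate of section 14.4. If the interval is too short, false claims become more likely than stated. Section 14.2 also says the data will be used to design later trials, so an understated standard error would carry forward.

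**Working it through.** **Plan figure.** The plan states no standard error, interval width or coverage for this model, so there is none to reproduce. The section 14.2 table enters only through its control proportion of 0.75.

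**Inputs from the plan.** 40 completers (14.2); 2x2 crossover with both eyes fitted (5.1); control proportion 0.75; margin 0.67, ln 0.67 = -0.400; two-sided 95% interval; Kenward-Roger.

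**Inputs assumed.** Logit-scale SDs for subject and subject-by-period; a pseudo-likelihood fit. Laplace and quadrature have no residual covariance matrix to model, so the combination in 14.5 and 14.6 points to pseudo-likelihood, but the plan does not say so.

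**Mechanism.** The linearised response is z = η + (y - μ)/[μ(1 - μ)]. Its residual variance is R scaled by 1/[μ(1 - μ)].
- Bernoulli: R = I, so the scale is 1.
- Planned CS, for the two eyes in one period: R = φ[(1 - ρ)I + ρJ], with φ and ρ free.
- Comparator: R = I, with the eye correlation carried by a subject-by-period random intercept.

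**Coverage at true odds ratio 1.** Restricted pseudo-likelihood, Kenward-Roger standard errors and degrees of freedom; 500 runs per row (400 at 90% response). SEs are medians; the empirical SD is that of the planned estimate.

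| SDs | Planned SE | Empirical SD | Planned coverage | SE, scale 1 | Coverage, scale 1 |
|---|---|---|---|---|---|
| 0.3/0.3 | 0.362 | 0.392 | 94.2% | 0.382 | 95.8% |
| 1/1 | 0.369 | 0.425 | 91.2% | 0.405 | 96.0% |
| 1/2 | 0.405 | 0.480 | 90.8% | 0.449 | 94.2% |
| 2/1 | 0.367 | 0.512 | 86.8% | 0.422 | 96.2% |
| 1/1, 90% response | 0.434 | 1.175 | 78.5% | 0.623 | 96.7% |

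Monte Carlo error is about 1.0 to 1.5 points for the first four rows and 2.1 for the last. A separate 250-run simulation at 2/1, without the Kenward-Roger variance adjustment, gave about 84-85% against 95-97%. With 200 subjects at 1/1 (200 runs), coverage was 94.0% against 95.0%.

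**Hand check.** Coverage is roughly 2Φ(t × SE/SD) - 1.
- 1/1: 2.023 × 0.369/0.425 = 1.756, giving 92.1%.
- 2/1: 2.021 × 0.367/0.512 = 1.449, giving 85.3%.

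Both agree with the table within Monte Carlo error.

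**Is the scale the cause?** At 1/1, (0.369/0.405)² = 0.83, in line with the typical median estimated scale of about 0.8 (range 0.5 to 0.86).

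**False non-inferiority at a true conditional odds ratio of 0.67 (nominal 2.5%).**

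| SDs | Planned | Scale 1 | Runs |
|---|---|---|---|
| 0.5/0.5 | 2.8% | - | 400 |
| 1/1 (with Kenward-Roger) | 3.2% | 1.8% | 600 |
| 1.0/0.5 | 5.0% | - | 400 |
| 1.5/1.0 | 5.5% | - | 400 |
| 2/1 | 7.0%, 7.2%, 8.8% | 4.0% | 400, 400, 250 |

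The 3.2% has a Monte Carlo error of 0.7 points, so it is not clearly above 2.5%. The 8.8% has an error of 1.8 points.

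**Width or bias?** Removing the mean bias lowered 5.0% to 3.7% and 5.5% to 4.3%. Part of the excess is therefore attenuation of the estimate.

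**The case against.** A reader might infer that the planned intervals simply are too narrow. The documents do not support that. They give no estimation method, no rule on the scale and no heterogeneity values. Undercoverage follows under the fit that the plan's ingredients imply, and its size follows from assumed SDs. With weak heterogeneity the loss cannot be told from simulation noise, and with 200 subjects it is small. This objection stands and sets the wording of the point. It does not remove it, because an unstated method and scale for the primary interval is itself a gap.

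A reader might also infer that the AICC choice between CS and UN is the fault. It hardly matters: AICC picked UN in at most 1% of runs, and in one comparison the two structures disagreed on non-inferiority in 2% of trials. The free scale is common to both candidates.

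Nor is the plan wrong to model the eye correlation. In one run at 1/2, adding the CS residual widened the interval compared with no eye term (mean SE 0.416 against 0.392), and both covered 91.6%. The comparator above keeps the eye correlation, so it is not a contrast between modelling and ignoring it.

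Finally, section 14.2 calls this a pilot not sized by a power analysis. That lowers the stakes, but section 14.5 still draws formal non-inferiority and superiority conclusions.

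**Conclusion.** The primary model is ill-specified for a binary outcome, and its interval can undercover at the planned size. Under a pseudo-likelihood fit with a free scale, 40 completers and the assumed SDs, coverage runs from about 94% (weak heterogeneity) to 84-87% (2/1), and to about 79% at 1/1 when response is near 90%. False non-inferiority at the margin ranges from about 3% to 9%, and not all of that comes from interval width. The direction is well supported; the size in this trial is unknown, because the plan gives nothing from which to set the SDs. The repair is cheap enough to make before database lock.

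**What to change.** In section 14.5, state the estimation method. Replace the residual CS/UN covariance and its AICC step with one pre-specified structure: random intercepts for subject within site and for subject-by-period, with the residual scale fixed at 1. Use it for both centration and movement, and keep Kenward-Roger. A marginal model with a small-sample-corrected robust standard error is an acceptable alternative; in one 600-run check at SDs 1.5/1.0, a cluster-robust marginal estimate had a two-sided error of 3.8%.

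The work is a change of wording and a short program change. There are two statistical costs:
- **Wider interval.** The SE rises about 10-15% in the middle cases (0.369 to 0.405 is 9.8%; 0.367 to 0.422 is 15.0%), 5.5% with weak heterogeneity, and 44% at 90% response.
- **More attenuation.** Against a true log odds ratio of -0.400, the mean estimate moved from -0.371 to -0.335 at 1.5/1.0 and from -0.368 to -0.307 at 2/1. That shift favours non-inferiority, so false non-inferiority may stay slightly above 2.5% (about 2-4% in these runs). The SAP should say so.

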14.6. Secondary Analysis

Secondary efficacy analysis:

CLUE handling scores will be analyzed using a linear mixed model adjusting for baseline values as fixed covariates. The model will include the experimental design factors: lens, period and lens by period interaction as fixed effects. Other baseline characteristics known to be important such as subject group (myope/hyperope), age, gender, and/or add power will be included as fixed covariates when appropriate. The covariance between residual errors from the same subject across lens wearing periods will be selected based on the finite-sample corrected Akaike's Information Criterion.⁶ Covariance structures considered may include: Homogenous compound symmetry (CS) and Unstructured covariance structure (UN). The structure that returns the lowest Akaike Information Criteria Corrected (AICC) will be selected as the structure that best fit the data.

Comparisons between the Test lens and Control lens will be carried out using 95% confidence intervals constructed of least-square means (LSM) differences (Test minus Control) from the linear mixed model. The non-inferiority of the Test lens relative to the Control will be concluded if the lower confidence limit of LSM difference is above the non-inferiority margin -5. The superiority will be established if the lower confidence limit is above 0.

In all models, the Kenward and Roger method⁶ will be used for the calculation of the denominator of degrees of freedom.

14.7. Other Exploratory Analyses

Not Applicable

14.8. Interim Analysis

Not Applicable

14.9. Procedure for Handling Missing Data and Drop-Outs

Missing or spurious values will not be imputed. The count of missing values will be included in the summary tables and listings.

Subject dropout is expected to be one of the main reasons of missing data in this clinical trial. Past clinical trials don't provide the evidence that subject dropout is systematic or not-at-random. To evaluate the impact of missing data, sensitivity analysis will be conducted using multiple imputation methods if the proportion of subject dropout is greater than the 15%. The SAS/STAT procedures PROC MI and PROC MIANALYZE will be utilized with a parametric regression method used to make at least 5 imputations.

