4.3. Enrollment Target and Study Duration

A total of approximately 50 eligible subjects will be enrolled with 40 targeted to complete the study. The study will last approximately 2-4 months.

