3.10	Lens Fit Assessment:	
Evaluate and grade lens centration, primary gaze movement, upgaze movement and tightness (push-up test).
 
 • The subject should not proceed to wear the lenses if any of the following is observed: • presence of limbal exposure (appearance of clear cornea) in any gaze • presence of edge lift • presence of unacceptable movement 	

		
(excessive or insufficient) in all three movement categories (primary gaze, upgaze, and push-up).
 
If either lens is deemed unacceptable, the subject will be discontinued from the study. Remove the lenses, perform a slit-lamp evaluation, and complete the Final Evaluation form.
	
3.11	Collection of unworn lenses (if applicable)	
If the first lens type fit on the subject was the daily disposable lenses collect unworn lenses returned by the subject.
	
3.12	Lens Removal	
Have the subject remove the study lenses and store in saline in a labeled glass vial.
 
Note: Lenses do not need to be stored in a refrigerator.
	
3.13	Biomicroscopy	
Perform biomicroscopy OD and OS. Slit Lamp Classification Scales will be used to grade the findings.
 
For the conjunctival redness [REDACTED] 0.5 unit increments will be used in the grading.
 
Corneal Staining Assessment [REDACTED] will be graded in 1.0 increments.
 
If the clearance of the fluorescein needs to be expedited, preservative-free rewetting drops or saline may be instilled.
	[REDACTED] [REDACTED] [REDACTED]
3.14	Distance and Near Exit Visual Acuity	
Distance and near Snellen visual acuity will be measured for each eye with the subject's habitual correction in place.
 
For near measures use the ETDRS 2000 Series Chart 1 or 2. The acuity will be recorded to the nearest letter OD, OS and OU.
	[REDACTED]
3.15	Schedule Follow-up	
The subject will be scheduled to return for their next appointment in 7 ± 3 days.
 
NOTE: Subject may wear their habitual spectacles or contact lenses during the washout period.
	

VISIT 4

The subjects may present to Visit 4 wearing their habitual spectacles or contact lenses, if required for their distance vision.

Visit 4: Baseline Treatment 2		
Step	Procedure	Details
4.1	Adverse Events and Concomitant Medications Review	
Review the subject's concomitant medications and record any changes from the previous study visit.
 
Record any adverse events or medical history changes from the previous study visit.

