8.2. Withdrawal/Discontinuation from the Study

A subject will be withdrawn from the study for any of the following reasons:

- Subject death during the study period
- Subject withdrawal of consent
- Subject not compliant to protocol
- Subject lost to follow-up
- Subject no longer meets eligibility criteria (e.g. the subject becomes pregnant)
- Subject develops significant or serious adverse events causing discontinuation of study lens wear
- Subjects who have experienced a Corneal Infiltrative Event (CIE)
- Investigator's clinical judgment regarding the subject safety reasons (that it is in the best interest of the subject to stop treatment)
- Subject missed two consecutive study visits
- Subject not compliant with study lens wear schedule
- Subject not successfully dispensed due to lack of efficacy and safety including poor vision, poor comfort or unacceptable fit

For discontinued subjects, the Investigator will:

- Complete the current visit (scheduled or unscheduled)
- Complete the Final Evaluation, indicating the reason that the subject was discontinued from the study
- Record the spherocylindrical refraction with best corrected distance visual acuity
- Collect used test article(s) (worn or brought to the visit) from the subject and discard them, unless otherwise stated in Section 6.7
- Collect all unused test article(s) from the subject

An additional subject may be enrolled if a subject discontinues from the study prematurely.

In cases where a subject is lost to follow-up, every possible effort must be made to contact the subject and determine the reason for discontinuation/withdrawal. The measures taken to follow up must be documented including two written attempts and a certified letter (or equivalent) as the final attempt.

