14. STATISTICAL METHODS

14.1. General Considerations

All data summaries and statistical analyses will be performed using the Statistical Analysis System (SAS) software Version 9.4 (SAS Institute, Cary, NC). Throughout the analysis of data, the results for each subject/eye will be used when available for summarization and statistical analysis. Unscheduled visits will be summarized separately and will be excluded from the statistical analysis.

Summary tables (Descriptive statistics and/or frequency tables) will be provided for all baseline variables, efficacy variables and safety variables as appropriate. Continuous variables will be summarized with descriptive statistics (n, mean, standard deviation [SD], median, minimum and maximum). Frequency count and percentage of subjects or eyes within each category will be provided for categorical data.

Summaries will be presented by study lens type and will be performed separately by completion status (Safety Population or Per-Protocol Population). All analyses will be conducted on per-protocol population (see Section 14.3).

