14.3. Analysis Populations

Safety Population:

All subjects who were administered any test article excluding subjects who drop out prior to administering any test article. At least one observation should be recorded.

Per-Protocol Population:

All subjects who have successfully completed all visits and did not substantially deviate from the protocol as determined by the trial cohort review committee prior to database hard lock (Per-Protocol Population). Justification of excluding subjects with protocol deviations in the Per-Protocol Population set will be documented in a memo to file.

Intent-to-Treat (ITT) Population:

All subjects regardless of actual treatment and subsequent withdrawal from study or deviation from protocol. At least one observation should be recorded.

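### As written, the dropout-triggered multiple imputation in Section 14.9 contains no dropouts, because Section 14.1 puts every analysis on the per-protocol set and no analysis uses the ITT set

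*Combined protocol and SAP*

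**What the plan says.** Four parts of the statistical section bear on this point.

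- **Section 14.9** says that missing values are not imputed in the main analysis, and names dropout as a main expected cause of missing data. To gauge its impact, "sensitivity analysis will be conducted using multiple imputation methods if the proportion of subject dropout is greater than the 15" per cent. The method is a parametric regression imputation with at least five imputations. No population is named.
- **Section 14.1** says "All analyses will be conducted on per-protocol population", without exception. Summaries are by lens type and "performed separately by completion status (Safety Population or Per-Protocol Population"); ITT is not mentioned.
- **Section 14.3** defines the per-protocol set as "All subjects who have successfully completed all visits" without substantial deviation. It defines ITT as "All subjects regardless of actual treatment and subsequent withdrawal from study or deviation from protocol", given at least one recorded observation.
- **Sections 14.5 and 14.6**, the primary and secondary analyses, name no population. Section 14.7 plans no exploratory analysis. Outside Section 14.3, ITT appears only in the abbreviation list.

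On numbers, Section 4.3 says "A total of approximately 50 eligible subjects will be enrolled with 40 targeted to complete the study". On reasons for leaving, Section 8.2 lists "Subject not successfully dispensed due to lack of efficacy and safety including poor vision, poor comfort or unacceptable fit".

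**The concern.** A sensitivity analysis for dropout has to contain the subjects who dropped out, or at least the data they left behind. Here the rule that sets the analysis population removes them before the imputation starts.

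This matters because dropout in this trial may be related to the primary endpoints, lens centration and movement. At Visit 3, step 3.10 tells the investigator to "Evaluate and grade lens centration, primary gaze movement, upgaze movement and tightness (push-up test"), and the same step discontinues a subject whose lens fit is unacceptable. Such a subject may have a primary endpoint grade on record at the right time point, yet never attends Visits 4 to 6 and so leaves the per-protocol set. A subject who finishes period 1 normally and leaves in period 2 loses a valid period 1 grade in the same way.

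Section 14.2 calls the study a pilot whose data will be used to design later trials. Sections 2.3 and 14.5 nevertheless set formal non-inferiority and superiority criteria on the odds ratio. Both uses rely on fit rates from completers.

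**Working it through.** **1. Which subjects are in the imputation dataset?** Setting the sections side by side:

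- Trigger (14.9): proportion of subjects dropping out above 15%.
- Population for all analyses (14.1): per-protocol.
- Per-protocol (14.3): every visit completed, no substantial deviation.
- Exception to 14.1 stated in 14.9: none.

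A dropout has not completed every visit. The number of dropouts in the dataset is therefore 0 at any dropout rate. The imputation is not necessarily empty, since a completer may have an isolated missing grade, but it cannot contain the subjects whose loss set it off.

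**2. Could the trigger fire?** Section 14.9 does not define the denominator, so two are shown.

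- Planned figures (4.3): 1 − 40/50 = 20%, above 15%.
- Exactly 40 completers, d dropouts, rate d/(40 + d): 7/47 = 14.9%, does not fire; 8/48 = 16.7%, fires.
- Exactly 50 enrolled, rate d/50: 7/50 = 14%, does not fire; 8/50 = 16%, fires.

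Either way the threshold is 8 dropouts. The documents give no expected dropout rate. Assuming a true rate p and independent dropout among 50 subjects, P(at least 8) from the binomial distribution is:

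| Assumed p | P(trigger fires) |
|---|---|
| 10% | 0.12 |
| 15% | 0.48 |
| 20% | 0.81 |

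**3. How many subjects are at issue?** With 50 enrolled and 40 completing, ITT could hold up to 50 − 40 = 10 dropouts who are absent from the per-protocol set, provided each has at least one recorded observation.

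**4. What recorded data would be set aside?**

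- Discontinued at step 3.10: possibly a Visit 3 grade of centration and movement, which is the primary time point for the first lens.
- Discontinued in period 2, for example at step 4.13 or 5.10 for unacceptable fit: a complete Visit 3 grade for the first lens.
- Discontinued after Visit 1 or 2: earlier fit grades from steps 1.27 and 2.10. These are not endpoint values but can inform an imputation.

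**5. Does anything else cover these subjects?** Section 14.1 plans summaries of efficacy variables on the Safety population, which keeps treated subjects who later leave. Section 14.9 plans counts of missing values, and final evaluation step F.1 records the reason for discontinuation. All of these are descriptive. No planned confidence interval for the odds ratio includes a dropout.

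**The case against.** The strongest reply is that Section 14.9 shows its own intent. It exists to assess dropout, and Section 14.3 defines a set that retains withdrawn subjects and has no other use, so a sensible analyst would join the two. That is probably what was meant. But Section 14.1 says all analyses, Section 14.9 states no exception, and Section 14.10 says the analysis will follow the sections as specified. Two analysts could defensibly run different datasets, and the choice would be made after the data are seen.

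Several stronger readings are tempting but not supported:

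- **That the planned numbers will fire the trigger.** The 50 is approximate, and 40 is a target in Section 4.3 and a minimum in Section 14.2. Replacement of discontinued subjects is allowed, and no dropout rate is given.
- **That the effect of dropout would go wholly unexamined.** The Safety-population summaries would show dropouts' recorded fit grades beside the per-protocol ones. What is missing is an inferential comparison that includes them.
- **That the non-inferiority conclusion would change.** The documents give no outcome rates for dropouts and no split by lens. Any figure would come from the assumptions put in, and a worst-case scoring of dropouts is not what regression-based imputation produces.
- **That every fit-related withdrawal is a missing primary outcome.** The Section 8.2 reason concerns subjects not successfully dispensed, for whom an endpoint after 6 to 8 days of wear is arguably undefined. The discontinuation criteria in step 3.10 also differ from a grade of not centered or not optimal.
- **That Visit 6 grades are lost in the same way.** A subject discontinued at Visit 6 has attended every visit and may count as a completer under Section 8.1.

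These points limit the size of the concern. They do not remove the conflict between Sections 14.1 and 14.9.

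**Conclusion.** Wrong as written. The sensitivity analysis meant to assess dropout is confined by Section 14.1 to subjects who did not drop out, and the one population that would serve it is left unused. This rests on reading Section 14.1 literally, which is the only reading the text states.

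In scale, up to 10 of 50 subjects (20%) are at issue on the planned figures, and the analysis would be called for at 8 or more dropouts. The possible link between dropout and the fit endpoints follows from the protocol's own discontinuation steps; whether any subject will leave that way is not known. Section 14.9's remark that past trials gave no evidence of systematic dropout does not rule out a mechanism written into this protocol. The size and direction of any effect on the odds ratio cannot be derived from the documents. The per-protocol primary analysis itself is not affected by this point.

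**What to change.** Add one or two sentences to Section 14.9:

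- State, as an exception to Section 14.1, that the multiple-imputation sensitivity analysis uses the ITT population defined in Section 14.3, and cross-refer from Section 14.1.
- Keep every recorded endpoint grade in that analysis, notably Visit 3 grades of subjects discontinued at Visit 3 or later.
- Allow earlier fit grades (steps 1.27 and 2.10 in period 1, step 5.10 in period 2) to inform the imputation.
- Specify a logistic imputation model for the 0/1 centration and movement endpoints. A regression method for continuous data would produce values other than 0 and 1.

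ITT also brings back completers excluded for deviations, so the report should say how many subjects are added for each reason.

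The cost is a short text change and a little programming. There are no new data, visits or changes to how subjects are managed.
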